3.3.3 Pharmacokinetics

Blood samples will be collected from subjects on study drug for treprostinil pharmacokinetic (PK) analysis. A venous or capillary blood sample, rather than arterial blood sample should be collected. Up to two samples will be taken from each subject:

- After 24 hours (+6 hours) of initiating study drug dosing (collected at least 2 hours after the last dose change)
- Immediately prior to beginning to down titrate (wean) study drug, or on Study Day 28 if the subject will continue on Remodulin

- A second sample is not required in subjects who are unblinded (after Day 14 or due to clinical worsening event) and identified to be on placebo

If any early or late blood draws are performed, the time and reason should be recorded in the eCRF. Appendix 15.2 contains a detailed description for the pharmacokinetic blood collection, processing, storage, and shipment of all samples.

3.4 NUMBER OF CENTERS

Approximately 40 centers are planned.

3.5 NUMBER OF SUBJECTS

Approximately 70 subjects will be randomized (1:1) to either receive treatment with Remodulin or placebo to provide 66 evaluable neonates. Enrollment will be closed once 66 evaluable subjects have been enrolled. No more than 32 subjects with a diagnosis of PPHN associated with CDH will be enrolled; these subjects will be evenly enrolled (1:1) into the Remodulin and placebo groups.

3.6 ESTIMATED STUDY DURATION

No subject will receive study drug for greater than 28 days (4 weeks). Post-treatment data will be collected until death, time of hospital discharge, time of study withdrawal, or until 4 weeks after last dose of study drug, whichever comes first. Subjects with ongoing AEs at the time of hospital discharge or study withdrawal will be followed for their AEs until either resolution (or return to normal or Baseline values), until judged by the Investigator to no longer be clinically significant, or for up to 4 weeks beyond the subject's last dose of study drug. Therefore, the maximum amount of time a subject randomized to study drug would be in the study is 56 days (a maximum of 28 days of study drug, plus 4 week follow-up (28 days) after last dose/discontinuing study drug). Per the Investigator's discretion, if Remodulin treatment is needed beyond Day 28, subjects will be transitioned to commercial product; Day 28 will be considered as the last day of study drug administration. These subjects will continue to be followed in the study until they have reached Day 56 (4 weeks after last dose of study drug), have been discharged from the hospital or withdrawn from the study, whichever comes first.

The study will be completed once 66 evaluable subjects have been enrolled and completed the last patient last visit/assessment.

4 SUBJECT ELIGIBILITY

4.1 INCLUSION CRITERIA

A subject is eligible to participate if the following criteria are met:

1. Parent(s) or legal guardian provides consent for the subject to participate, as per institutional policy.
2. Weight at least 2 kg at Screening.
3. Gestational age of at least 34 weeks and is \leq 14 days old at Screening.
4. Diagnosis of PPHN, which is either idiopathic in nature or associated with the following: MAS, pneumonia, RDS, sepsis, birth hypoxia, perinatal encephalopathy or unilateral CDH.
5. Currently requiring ventilator support.
6. Two consecutive OIs of 15 or greater separated by at least 30 minutes, after receiving iNO for at least 3 hours.
7. Echocardiographic evidence of PH (e.g., ductal shunting, significant TR) with elevated RV pressures).
8. Have venous access (central line or peripherally inserted central venous catheter [PICC, PCVC]) for the administration of study drug. In the event central venous access cannot be established or in the opinion of the Investigator the patient is too unstable to attempt to establish a central venous access line for IV administration of study drug, subjects who are candidates for administration of study drug as a continuous SC infusion may be enrolled.

4.2 EXCLUSION CRITERIA

A subject is ineligible for participation if any of the following criteria are met:

1. Previous or concurrent use of a PDE-5i, ERA or prostanoid. Previous receipt of prostaglandin E1 for ductal patency is allowed.
2. Significant congenital heart disease (CHD) as detected by ECHO (excluding presence of minor defects such as small secundum ASD, minor valvular abnormalities, or expected transitional findings such as a PFO, or PDA. Subjects with small muscular, restrictive VSD may be enrolled).
3. Clinically significant, untreated active pneumothorax at Screening.
4. Evidence of clinically significant bleeding (e.g., hemodynamic instability or requiring transfusion) at Screening. Note: history of a transfusion is not necessarily an exclusion criterion.
5. Necrotizing enterocolitis; defined as Bells stage II or greater at Screening.
6. Uncontrolled hypotension; defined as mean systemic pressures less than or equal to 35mmHg at Screening.

7. Uncontrolled coagulopathy and/or untreated thrombocytopenia; defined as <50,000 platelets / μ L at Screening.
8. History of severe (Grade 3 or 4) intracranial hemorrhage at Screening. Note: a cranial ultrasonography is not required during Screening.
9. Currently receiving ECMO or has immediate plans to initiate ECMO.
10. Expected duration on mechanical ventilation of less than 48 hours.
11. Life expectancy is less than two months or has a lethal chromosomal anomaly.
12. Contraindication to ECMO.
13. Bilateral congenital diaphragmatic hernia.
14. Active seizures at Screening.
15. Currently participating in another clinical drug study (excluding observational registries).

4.3 PRESCRIBED THERAPY

4.3.1 *Concomitant Medications*

All subjects will be concurrently receiving iNO prior to randomization. Subjects should be adequately treated (as determined by the Investigator) with standard of care treatments for PPHN (e.g., inotropes, opioids, sedation) prior to enrollment and during the study. Doses of medications should be adjusted as needed during the study. All concomitant medications will be recorded in the subject's eCRF up until 48 hours after discontinuation of study drug. Any concomitant medications used in the treatment of an AE or SAE will be recorded even if it occurs more than 48 hours after discontinuation of study drug.

Caution should be used with cytochrome P450 (CYP) 2C8 enzyme inducers/inhibitors, such as rifampin or gemfibrozil, as plasma concentrations of treprostinil may be altered. Concomitant administration of Remodulin with diuretics, antihypertensive agents or other vasodilators may increase the risk of symptomatic hypotension. Remodulin inhibits platelet aggregation, there may be an increased risk of bleeding when administered with other anticoagulants, such as warfarin, heparin, or NSAIDs.

4.3.1.1 *Inotropic Dose Changes*

Doses of inotropic and vasoactive agents (e.g., dopamine, epinephrine, dobutamine, milrinone, vasopressin, norepinephrine) will be recorded with each dose change of study drug.

4.3.1.2 *Initiation of a Pulmonary Vasodilator Therapy*

If the Investigator initiates a targeted pulmonary vasodilator (after meeting the requirements outlined in Section 3.3.1.1.1) during the first 14 days after randomization, the subject will meet the definition of the primary endpoint of clinical worsening.

Subjects randomized to study drug who meet the definition of clinical worsening may continue to receive study drug for a total of up to 28 days at the discretion of the Investigator.

5 SUBJECT ENROLLMENT

5.1 TREATMENT ASSIGNMENT

Subjects will be randomized (1:1) to receive treatment with Remodulin or placebo.

5.2 RANDOMIZATION

An Interactive Web Response System (IWRS) will be utilized for the central randomization procedure. Subjects will be randomized in a ratio between active and placebo of 1:1. No more than 32 evaluable subjects with a diagnosis of PPHN associated with CDH will be enrolled; these subjects will be balanced between the treatment groups.

5.3 BLINDING

This will be a double-blind, placebo controlled study. Subjects will be randomly allocated to Remodulin or placebo via an IWRS system. Investigators, research staff, attending clinicians, NICU staff, and parents will remain blind to the treatment allocation, unless certain criteria for unblinding are met. Some differences in packaging of investigational product may be observed during the study, but pharmacy personnel will not be made aware of the actual treatment assignment. The pharmacist must not communicate with the Investigator or any members of the clinical team about the appearance of vials used in dose preparation. No additional packaging or wrapping is required prior to dispensing the prepared syringe to the floor. Once prepared, the appearance of active and placebo doses are identical.

Access to treatment assignment is outlined in Section 6.2.

6 DRUGS AND DOSING

6.1 DRUG DOSAGE, ADMINISTRATION AND SCHEDULE

6.1.1 *General Information*

Study drug (Remodulin or placebo) will be supplied in multiple-dose 20mL glass vials containing 1mg/mL treprostinil or placebo. Vials are multi-use and may be used up to 30 days after initial puncture to prepare multiple doses/syringes for the assigned subject. A new vial should be used for each subject.

6.1.2 *Dose and Administration of Study Drug*

This study aims to evaluate Remodulin administered as a continuous IV infusion in a neonate population. A venous access (preferred via central line (e.g., umbilical venous catheter [UVC] or peripherally inserted central venous catheter [PICC, PCVC]) is required for the IV administration of study drug. Currently, there are no data to confirm whether Remodulin is compatible and may be administered in the same line/lumen with other IV administered agents; however, compatibility studies are planned. Therefore, one line or lumen must be dedicated solely to study drug when administering as a continuous IV infusion until the Investigator is notified by United Therapeutics of the outcome of the compatibility studies. Once compatibility with other IV agents has been confirmed, study drug may be administered in accordance with the data provided. If clinically necessary, a temporary peripheral IV cannula, preferably placed in a large vein, may be used (Remodulin Package Insert or Summary of Product Characteristics). However, use of a peripheral IV infusion may be associated with an increased risk of thrombophlebitis and administration should be short term (Remodulin Package Insert or Summary of Product Characteristics).

In the event dedicated central venous access cannot be established, or in the opinion of the Investigator the patient is too unstable to attempt to establish a dedicated central venous access line for IV administration of study drug, study drug may be initiated as a continuous SC infusion at the discretion of the Investigator. Subjects initiated on IV administration of study drug who lose venous access may be transitioned to SC administration. Remodulin is bioequivalent between the SC and IV route. Therefore, no dose adjustment in study drug is needed if the SC route is utilized (16, 17).

Study drug must be diluted with high-pH glycine diluent (Sterile Diluent for Remodulin, Sterile Diluent for Flolan, or Sterile Diluent for Epoprostenol Sodium), Sterile Water for Injection, or 0.9% Sodium Chloride Injection, prior to IV administration as a continuous infusion using an infusion pump designed for intravenous drug delivery.

Diluted Remodulin has been shown to be stable at ambient temperature for up to 52 hours at concentrations as low as 0.00025mg/mL (250ng/mL) (e.g., infusion cassettes/syringes should be changed at least every 48 hours).

If study drug will be administered as a continuous SC infusion, dilution of study drug is usually not required; however, based upon the selected SC infusion pump flow rate capabilities, the subject's dose weight, and dose in this neonate patient population, dilution may be needed for SC administration (especially for smaller babies and lower doses, or during weaning of study drug). If dilution is required for SC administration, Sterile Water for Injection or 0.9% Sodium Chloride for Injection should be used.

Do not flush study drug line and use caution when changing the study drug infusion line to avoid an accidental bolus/overdosage.

6.1.2.1 Calculating the Study Drug Dilution

Prior to calculating the subject dose of study drug, the following information is needed: volume of infusion syringe or cassette, dose (ng/kg/min; nanogram/kilogram/minute) and weight (kg). The starting dose is 1ng/kg/min. The subject's weight from Baseline should be used to calculate the dose throughout the study period.

Study drug will be diluted to the appropriate concentration depending on the individual's dose and infusion rate for intravenous, or subcutaneous (if applicable) infusion. A separate study drug preparation form may be used to document preparation of dilutions.

Step 1: Calculate the concentration of the dilution to prepare based on subject's Baseline weight, dose and infusion rate

$$\text{Diluted study drug conc. } \left(\frac{\text{mg}}{\text{mL}} \right) = \frac{\text{dose (ng/kg/min)} \times \text{Weight (kg)} \times 0.00006^*}{\text{infusion rate } \left(\frac{\text{mL}}{\text{hr}} \right)}$$

* Conversion factor of 0.00006 = 60 min/hour x 0.000001 mg/ng

Next, the amount of study drug from the 1mg/mL study drug vial needed to make the required diluted concentration for the given syringe size can be calculated using the following formula:

Step 2: Calculate the amount of study drug need to prepare the desired concentration

$$\text{Amount of study drug (mL)} = \frac{\text{Diluted study drug conc. (mg/mL)} \times \text{Syringe Volume (mL)}}{1 \text{ mg/mL Vial Strength}}$$

The calculated amount of study drug from the 1mg/mL vial is then added to the reservoir along with the sufficient volume of diluent to achieve the desired total volume in the syringe pump.

Study drug may be continually titrated (i.e. up-titration and weaning) during the course of the trial. There will be multiple dose titrations occurring and the choice in concentration should be able to account for multiple titrations to limit the amount of times an infusion syringe or cassette must be prepared or changed.

The concentration should be increased when the volume required to deliver the dose exceeds the ideal fluid intake. Increasing the concentration will decrease the flow rate and volume of study drug administered while allowing for continued dose titrations.

6.1.3 Dose Initiation and Titration

The starting dose of study drug is 1ng/kg/min, which is not anticipated to provide clinical effects. The dose of study drug should be increased by up to 2ng/kg/min every 2 hours, as tolerated and clinically indicated by the physician, based upon the OI; when the OI is no longer calculable, the FiO₂ will be used to guide dosing. As some subcutaneous infusion pumps may not accommodate a starting dose of exactly 1ng/kg/min, the site may proceed with a starting dose as close to 1ng/kg/min as possible. The initial starting dose should not exceed 2ng/kg/min and should be increased by approximately 1-2ng/kg/min every 2 hours as tolerated and clinically indicated by the

physician. Subject response to study drug is individualized; not all subjects will tolerate the same rate of titration and clinically beneficial doses will vary. There is no maximum dose limit. Titration will be made per the subject's response in clinical symptoms.

If the OI is 15 or greater, the dose of study drug should be increased in the absence of dose-limiting adverse events (e.g., hypotension). If the OI is between 10 -14 and the study drug dose is ≤ 10 ng/kg/min, the dose should continue to be increased, as tolerated. If the study drug dose is >10 ng/kg/min and the OI is between 10 -14, any further dose escalation will be left to the discretion of the clinicians/Investigators according to the clinical condition of the subject, and the perceived need for additional pulmonary vasodilation. Once the OI is <10 and iNO has been discontinued, study drug weaning can begin (Section 6.1.4).

If the OI cannot be calculated, dose adjustments will be based upon FiO₂. The study drug dose should be increased when the FiO₂ is $\geq 60\%$ in the absence of dose-limiting adverse events (e.g., hypotension). Once the FiO₂ is $<60\%$ and iNO has been discontinued, weaning of study drug can begin. Table 6-1 below describes the suggested dose titration parameters.

Table 6-1 Suggested Study Drug Dose Titration Parameters

Oxygenation Index	FiO ₂ (To be used when OI is not calculable)	Dosing Strategy
≥ 15	$\geq 60\%$	Dose increase, as tolerated
10-14 (dose >10 ng/kg/min)	--	Hold dose or dose increase if clinical condition warrants further pulmonary vasodilation.
10-14 (dose ≤ 10 ng/kg/min)	--	Dose increase, as tolerated
<10	$<60\%$	Begin weaning. The iNO should be weaned and discontinued prior to initiating weaning of study drug.

Subjects may continue on study drug for up to 28 days if clinically indicated. Per the investigator's discretion, if the subject is treated with Remodulin beyond Day 28, Day 28 will be considered as the last day of study drug administration. These subjects will continue to be followed in the study until they have reached Day 56 (4 weeks after last dose of study drug) or have been discharged from the hospital, whichever comes first.

6.1.4 *Dose Weaning*

Abrupt cessation of study drug will be avoided due to the risk of rebound pulmonary hypertension. Inhaled NO should be weaned and discontinued prior to initiating weaning of study drug. When the subject has reached the treatment goal and is ready to start weaning, the dose of study drug will be held constant at the same dose for at least 12 hours prior to initiating down titration. It is recommended the dose of study drug be decreased by no more than 10ng/kg/min per day either in the same incremental manner as the dose was increased or as determined by the Investigator. Dose decreases in increments greater than 5ng/kg/min are recommended to be avoided, but faster weaning may occur if required per subject care.

If withdrawal from study drug is warranted, the dose of study drug will be weaned until discontinued.

6.1.5 *Initiation of ECMO*

Subjects randomized to study drug may continue to receive study drug during ECMO at the pre-ECMO dose. Subjects should not be unblinded upon initiation of ECMO, unless required for purposes of medically managing the subject. At the conclusion of ECMO, weaning of study drug can begin per the Investigator's discretion.

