7.3.3.3 Study Drug Discontinuation

The following will be collected immediately (within 12 hours) after study drug discontinuation.

- Physical examination
- Vital signs (BP, RR, HR, Temp, SpO₂)
- FiO₂
- MAP (if the subject is on mechanical ventilation)

- Clinical laboratory assessments (See Section 3.3.2.3)
- NT-proBNP
- Blood gasses (if arterial access is not available, collect CBGs/VBGs)
- Record concomitant medications (until 48 hours after the subject has stopped receiving study drug)
 - Record doses of inotropes
- Record AEs

These assessments will not be performed in subjects who continue on commercial Remodulin beyond Day 28.

7.3.3.4 48 Hours after Study Drug Discontinuation

The following will be collected 48 hours \pm 4 hours after study drug discontinuation.

- Vital signs
- Clinical laboratory assessments (See Section 3.3.2.3)
- Echocardiogram
- Record concomitant medications (until 48 hours after the subject has stopped receiving study drug)
 - Record doses of inotropes
- Record AEs

These assessments will not be performed in subjects who continue on commercial Remodulin beyond Day 28.

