9.3 PERIOD OF OBSERVATION

For the purposes of this study, the period of observation starts from the time the informed consent is signed and concludes upon meeting screen failure criteria, at the time of death, at the time of hospital discharge, at the time of withdrawal from the study, or at 4 weeks after last dose of study drug, whichever comes first. Day 28 will be considered as the last day of study drug administration for subjects who continue on Remodulin. Subjects with ongoing AEs at the time of hospital discharge will continue to be followed for their AEs until either resolution (or return to normal or Baseline values), until judged by the Investigator to no longer be clinically significant, or until 4 weeks after last dose of study drug. All SAEs should be followed until resolution, death, or the subject is lost to follow-up, even if they are ongoing more than 4 weeks after the last dose of study drug.

If the subject receives commercial Remodulin after hospital discharge, beyond Day 56/End of study, or following withdrawal from the study, AEs/SAEs will be subject to AE/SAE reporting under local government post-marketing AE/SAE reporting requirements.

Supplemental measurements and/or evaluations may be necessary to investigate fully the nature and/or causality of an AE or SAE. This may include additional laboratory tests, diagnostic procedures, or consultation with other healthcare professionals. The eCRF pages should be updated with any new or additional information as appropriate.

If the Investigator detects an SAE in the study subject after the end of the period of observation, and considers the event possibly related to prior study treatment, he or she should contact the Sponsor to determine how the event should be documented and reported.

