12.1 EXTENT OF EXPOSURE

A listing of study drug dosing will include route of administration (IV or subcutaneous); initial dose and date and time of initial dose; and dose, date, and time of each dose change. Overall

duration of exposure will be included as well as the final dose and the maximum study drug dose reached for each subject. Summaries of initial dose, final dose, and maximum dose will be provided by treatment group. If the data warrant, these summaries will also be produced by route of administration.

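### For infants who stay on commercial Remodulin after Day 28, AEs are counted to Day 56 but treprostinil dose, stop date and exposure days are not, so the AE rate is mismatched and late AEs cannot be linked to dose or withdrawal

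*Protocol*

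**What the plan says.** **Supply changes at Day 28.** Protocol 3.6 says "if Remodulin treatment is needed beyond Day 28, subjects will be transitioned to commercial product". Section 6.1.3 sets the last-dose convention: "if the subject is treated with Remodulin beyond Day 28, Day 28 will be considered as the last day of study drug administration". Section 9.3 repeats it for the AE observation period: "Day 28 will be considered as the last day of study drug administration for subjects who continue on Remodulin".

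**Follow-up continues.** Protocol 3.6: "These subjects will continue to be followed in the study until they have reached Day 56", unless discharge or withdrawal comes first. Section 7.3.4 schedules a Day 56 final assessment for them. Under 3.3.2.4 and 9.3, AEs on Remodulin pass to post-marketing reporting only after discharge, after Day 56 or after withdrawal, so in-hospital AEs from Day 29 to Day 56 are study AEs.

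**Stop-related assessments are waived.** Section 7.3.3.3, on the visit at discontinuation: "These assessments will not be performed in subjects who continue on commercial Remodulin beyond Day 28". Sections 7.3.3.2 and 7.3.3.4 and footnotes p and q of Table 3-1 do the same for the daily weaning visits and the 48-hour visit. The pre-wean set is done on Day 28 instead (7.3.3.1).

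**Medication capture closes.** Footnote m and section 4.3.1 end routine concomitant-medication recording 48 hours after study drug stops. The exception is in 4.3.1: "Any concomitant medications used in the treatment of an AE or SAE will be recorded", even after that point.

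**Analysis.** SAP 12.1 lists study-drug dosing, where overall "duration of exposure will be included as well as the final dose and the maximum study drug dose reached for each subject". SAP 12.2 defines a treatment-emergent AE as one starting on or after first dose, with no end date. Its AE rate is the number of AEs divided by patient-days of exposure to study drug in each group.

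**The concern.** When an infant moves to commercial Remodulin the molecule stays the same; only the supply changes. The plan nevertheless stops counting exposure at Day 28 while it goes on counting AEs. Two things follow.

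First, the AE rate in SAP 12.2 takes its events from a longer period than its days. For a continuing infant the extra period is time on treprostinil, so real drug days are missing from the denominator while the AEs in those days are in the numerator.

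Second, no section requires the commercial dose, its changes or its stop date to be recorded once medication capture has closed. Protocol 6.1.4 names rebound pulmonary hypertension as the risk of abrupt cessation. If such an infant is weaned in hospital before Day 56, the database need not show when, or from what dose. Protocol 6.1.3 also sets no dose ceiling, so the final and maximum doses in SAP 12.1 could both miss a later, higher commercial dose.

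The infants concerned are those with the longest courses. Protocol 7.3.4 describes them as infants randomized to Remodulin, so the missing drug days fall in one arm.

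**Working it through.** **Inputs from the documents**
- Maximum study-drug days: 28 (Protocol 3.6).
- Maximum follow-up after last dose: 28 days (Protocol 3.6).
- Routine medication capture after study drug: 48 hours, i.e. 2 days (footnote m, section 4.3.1).
- Infants per arm: 33 (Protocol 10.2).
- AE rate = AEs / study-drug patient-days (SAP 12.2).

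**Inputs assumed, because the documents do not give them**
- Number of infants who continue to Day 56 on commercial drug, in hospital: k = 0, 1, 3, 5, 10.
- Mean study-drug days in the other 33 − k infants: m = 5, 7, 14.

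**Step 1. The plan's own figure.** Maximum time in study = 28 + 28 = 56 days, as Protocol 3.6 states.

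**Step 2. Days with no required treprostinil record, per continuing infant.** Day 29 to Day 56 is 56 − 28 = 28 days. Medication capture covers about 2 of them, leaving 28 − 2 = 26. This is a maximum; discharge, withdrawal or death shortens it. The closing date of about Day 30 comes from reading footnote m together with the Day 28 rule; no section states it.

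**Step 3. AE rate for one continuing infant.** With a constant rate r per day, expected AEs to Day 56 are 56r. The counted denominator is 28 days. The computed rate is 56r/28 = 2.0r, an overstatement of up to 2-fold.

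**Step 4. Arm-level day counts.** Counted days = (33 − k)m + 28k. Treprostinil days = counted days + 28k. Example with k = 3, m = 7: counted = 30×7 + 84 = 294; treprostinil = 294 + 84 = 378; ratio 378/294 = 1.29.

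| k | m = 14 | m = 7 | m = 5 |
|---|---|---|---|
| 0 | 1.00 | 1.00 | 1.00 |
| 1 | 504/476 = 1.06 | 280/252 = 1.11 | 216/188 = 1.15 |
| 3 | 588/504 = 1.17 | 378/294 = 1.29 | 318/234 = 1.36 |
| 5 | 672/532 = 1.26 | 476/336 = 1.42 | 420/280 = 1.50 |
| 10 | 882/602 = 1.47 | 721/441 = 1.63 | 675/395 = 1.71 |

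**Step 5. What the ratios do and do not show.** They isolate the uncounted commercial-drug days. They equal the inflation of the arm's AE rate only if every other infant contributes AEs from drug days alone. The open-ended definition does not ensure that. An infant with 14 study-drug days and the full 28 days of follow-up also has (14 + 28)/14 = 3.0 AE-collection days per counted day, in either arm. The net effect on the comparison between arms therefore cannot be computed from the documents.

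**The case against.** The strongest reply is that the Day 28 convention is coherent in its own terms. Study drug is capped at 28 days, SAP 12.1 reports study drug, and commercial treatment afterwards is the investigator's choice. Footnote q waives the stop visits because no stop has occurred at Day 28. The safety purpose that Protocol 3.1 gives for extended dosing covers the additional 14 days of study drug, not commercial use afterwards. The number of continuing infants may be zero, safety summaries are descriptive (Protocol 10.3.3), and the primary endpoint closes at Day 14. All of this stands, and it limits the weight of the point.

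It also rules out two stronger readings that a reader might infer.

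- *That AEs on commercial drug are analysed as off-drug events.* Protocol 3.6 does use that label for data after the last dose: "Post-treatment data will be collected until death, time of hospital discharge, time of study withdrawal". But the SAP has no post-treatment category. Its definition keeps these AEs in the treatment-emergent summaries, so they are not hidden.
- *That a later rebound would leave no trace.* Under Protocol 9.2 a reported AE carries onset and cessation date and time. SAE forms come with relevant hospital records (9.4), and drugs used to treat an AE are still recorded. The concomitant-medication listing in SAP 9.3.3 also has a stop-date or ongoing field, so the start of commercial drug may be captured within the 48 hours. Nothing requires that entry to be updated later.

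The reply does not remove the mismatch in the SAP 12.2 rate or the missing dose and stop date. Calling the denominator study-drug days does not repair a rate whose numerator runs on for up to 28 more days of treprostinil.

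**Conclusion.** The concern holds as a defect of exposure recording and rate definition. Following the plan exactly, an infant on commercial Remodulin to Day 56 has up to 28 treprostinil days outside counted exposure, of which up to about 26 have no required dose or stop-date record. At a constant event rate that infant's AE rate is overstated up to 2-fold.

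For the arm, treprostinil days exceed counted days by a factor of 1.06 to 1.71 for 1 to 10 continuing infants, and by nothing if there are none. Those factors assume 33 infants, a mean of 5 to 14 study-drug days in the others, and every continuing infant in hospital on drug to Day 56.

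A late AE, possible rebound included, is dated but cannot be tied to treprostinil dose or withdrawal. Power and the primary endpoint do not change. The point should be corrected, but it does not threaten the trial's main conclusion.

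**What to change.** **Protocol, Table 3-1 footnote m and sections 4.3.1 and 6.1.3.** For infants moved to commercial Remodulin, require dose, each dose change, and stop date and time to be recorded until Day 56, discharge or withdrawal, whichever comes first.

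**SAP 12.1.** Keep the study-drug exposure summary and add a row for study drug plus commercial Remodulin.

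**SAP 12.2.** Flag each AE from Day 29 as on or off treprostinil. Compute AE rates with matching numerator and denominator: on-treprostinil AEs over total treprostinil days in the Remodulin arm, with the same on-treatment convention for AEs and infusion days in the placebo arm. This also removes the general mismatch shown in step 5 of the working. The treatment-emergent incidence tables can stay as they are.

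The Day 28 label can remain for supply and visit scheduling. No dosing or weaning rule is proposed.

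**Cost.** A little extra data entry for what may be very few inpatients, plus short additions to SAP 12.1 and 12.2.
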